10.2.3 Analysis of Long Term Adverse Event Rates

Long term adverse event rates will be analyzed using event rates adjusted by cumulative exposure and will be based on the actual treatment received at the time of AE occurrence. The detailed treatment groups are defined as follows.

1. Upadacitinib (ABT-494) 7.5 mg QD

This includes AEs occurred under Upadacitinib 7.5 mg QD exposure from subjects starting on Upadacitinib 7.5 mg QD and subjects switching from placebo to Upadacitinib 7.5 mg QD.

2. Upadacitinib (ABT-494) 15 mg QD

This includes AEs occurred under Upadacitinib 15 mg QD exposure from subjects starting on Upadacitinib 15 mg QD and subjects switching from placebo to Upadacitinib 15 mg QD.

3. Upadacitinib (ABT-494) 30 mg QD

This includes AEs occurred under Upadacitinib 30 mg QD exposure from subjects starting on Upadacitinib 30 mg QD and subjects switching from placebo to Upadacitinib 30 mg QD.

4. Placebo

10.2.3.1 Overview of Adverse Events Rates per 100 Patient-Years of Study Drug Exposure

An overview of AEs per 100 patient-years of study exposure will be presented by treatment group and overall for the following AE categories.

- All TEAEs
- Treatment-emergent serious adverse events (SAEs)
- Treatment-emergent severe adverse events

- TEAEs reasonably possibly related to study drug
- TEAEs of special interest
- TEAEs leading to discontinuation of study drug
- TEAE leading to death

For this calculation, 1 year will be considered to be 365.25 days. For each treatment group, the numerator of the overall rate will be the total number of TEAEs reported for the event; that is, a subject can contribute more than one event to the numerator. For each treatment group, the denominator of the rates will be the total number of days exposed to study drug summed across all treated subjects divided by 365.25. Please refer to Section 8.0 for the calculation of study drug exposure. The AE rate per 100 patient-years of exposure will be calculated as $([\text{numerator}/\text{denominator}]) * 100$. The number of AEs reported (numerator), the total number of years of study drug exposure (denominator), and the AE rate per 100 patient-years will be presented for each treatment group and overall.

Additional AEs may be considered for tabulation/summary based on recommendations from Clinical and Safety as deemed appropriate.

For TEAEs of special interest, the point estimate and 95% CI (using normal approximation) will be provided for the treatment difference in AE rate per 100 patient-years between each Upadacitinib dose group and the combined placebo group.

10.2.3.2 Adverse Events Rates per 100 Patient-Years of Study Drug Exposure by SOC and PT

For each treatment group, the TEAE rate per 100 patient-years of exposure will be calculated overall, for each SOC and each PT, for each of the following events:

- All TEAEs
- Treatment-emergent serious adverse events (SAEs)
- Treatment-emergent severe adverse events
- TEAEs reasonably possibly related to study drug
- TEAEs leading to discontinuation of study drug

- TEAE leading to death
- TEAEs of special interest

For this calculation, 1 year will be considered to be 365.25 days. For each treatment group, the numerator of the overall rate, the SOC rate, or the PT rate, will be the total number of TEAEs reported overall, for the SOC, or for the PT, respectively; that is a subject can be counted more than once overall, for a SOC, and for a PT. For each treatment group, the denominator of the rates will be the total number of days exposed to study drug summed across all treated subjects divided by 365.25. Please refer to Section 8.0 for the calculation of study drug exposure. The AE rate per 100 patient-years of exposure will be calculated as [(numerator/denominator)]*100. The number of AEs reported (numerator), the total number of years of study drug exposure (denominator), and the AE rate per 100 patient-years will be presented overall, for each SOC, and for each PT for each treatment group.

10.2.3.3 Adverse Events of Special Interest Rates per 100 Patient-Years of Study Drug Exposure

The Adverse Events of Special Interest (AESI) categories will be summarized and presented for each treatment group and overall using SOC and MedDRA PT. The AESI categories will be identified per Standard MedDRA Queries (SMQs)/Company MedDRA Queries (CMQs).

For each treatment group, the Adverse Events of Special Interests (AESI) rate per 100 patient-years of exposure will be calculated overall, for each SOC and each PT, for each of the AESI listed in Section 10.2.2.6.

For this calculation, 1 year will be considered to be 365.25 days. For each treatment group, the numerator of the overall rate, the SOC rate, or the PT rate, will be the total number of TEAEs reported overall, for the SOC, or for the PT, respectively; that is a subject can be counted more than once overall, for a SOC, and for a PT. For each treatment group, the denominator of the rates will be the total number of days exposed to

study drug summed across all treated subjects divided by 365.25. Please refer to Section 8.0 for the calculation of study drug exposure. The AE rate per 100 patient-years of exposure will be calculated as [(numerator/denominator)]*100. The number of AEs reported (numerator), the total number of years of study drug exposure (denominator), and the AE rate per 100 patient-years will be presented overall, for each SOC, and for each PT for each treatment group.

10.2.3.4 Listing of Serious Adverse Events (Including Deaths) and Adverse Events Leading to Study Drug Discontinuation

All serious adverse events (SAEs), deaths, and adverse events leading to discontinuation of study drug will be listed.

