#### **5.6.4 Selection of Doses in the Study**

Three doses of the once-daily formulation of upadacitinib will be evaluated: upadacitinib 7.5 mg QD, 15 mg QD and 30 mg QD. The dose selection in this study is based on extrapolation of pre-clinical efficacy models and analyses of PK, pharmacodynamic, safety, and efficacy data from the Phase 1 studies in healthy volunteers (single and multiple ascending dose Studies M13-401 and M13-845, respectively, and Asian Study M13-543) and Phase 2 studies in RA subjects (Studies M13-537 and M13-550). The doses selected for Study M14-663, upadacitinib 7.5 mg QD, 15 mg QD and 30 mg QD, dosed for approximately 3 years and half are expected to be efficacious with an acceptable safety profile.

The once-daily formulation (tablet) of 7.5 mg, 15 mg and 30 mg QD doses to be used in this study are expected to have comparable daily AUC and  $C_{trough}$  to the 3 mg BID, 6 mg BID and 12 mg BID immediate release doses (capsule) used in the global Phase 2 studies, respectively. In Phase 2 studies, the 6 mg BID dose was shown to achieve the near maximum efficacy and the 12 mg BID dose was clearly shown to achieve the plateau of efficacy.

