### **8.1.5.2.1 Treatment-Emergent Adverse Events (TEAE)**

AEs will be coded using MedDRA. A TEAE is defined as AE that began or worsened in severity after initiation of study drug.

AEs starting more than 30 days following the last dose of study drug will not be included in summaries of TEAEs. For subjects who continued into Period 2, the AEs that are reported in Period 2 will be captured in the combined safety analysis of Period 1 and Period 2.

As a general safety summary, the number and percentage of subjects experiencing TEAEs will be summarized for each treatment group for the following AE categories:

- All AEs;
- All severe AEs;
- All reasonably possibly related AEs;
- All SAEs;
- Frequent AEs (reported in 5% of subjects or more in any treatment group);
- Frequent reasonably possibly related AEs (reported in 5% of subjects or more in any treatment group);
- Discontinuations due to AEs;
- Death.

Additional AEs may be considered for tabulation/summary based on recommendations from Clinical and Safety as deemed appropriate.

TEAEs will be summarized and presented by system organ classes (SOCs) and preferred terms (PTs) using MedDRA. The SOCs will be presented in alphabetical order, and the PTs will be presented in alphabetical order within each SOC.

TEAE will also be summarized by maximum severity and by maximum relationship.

The AEs of special interest (including but not limited to serious infection, opportunistic infection, malignancy, non-melanoma skin cancer (NMSC), malignancy other than NMSC, lymphoma, hepatic disorder, gastrointestinal perforation, anemia, neutropenia, lymphopenia, herpes zoster, increased CPK, renal dysfunction, tuberculosis, adjudicated cardiovascular events and embolic and thrombotic events (non-cardiac, non-CNS) will be summarized. Event rate (per 100 patient years) for AEs of special interest will also be summarized for the combined safety analysis of Period 1 and Period 2.

All AEs leading to discontinuation of study drug will be presented in listing format. A listing by treatment group of TEAEs grouped by SOC and MedDRA preferred term with subject identification numbers will be generated.

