4.4 Interim Analysis

An unblinded analysis will be conducted after all subjects have completed Period 1 (Week 12). Additional unblinded analyses may be conducted for the purpose of regulatory submission. Study sites and subjects will remain blinded for the duration of the study (Periods 1 and 2).

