10.2.2.1 Adverse Events Overview

The number and percentage of subjects experiencing TEAEs will be summarized by "as treated" treatment group and overall for the following AE categories.

- All TEAEs
- Treatment-emergent serious adverse events (SAEs)
- Treatment-emergent severe adverse events
- TEAEs reasonably possibly related to study drug
- TEAEs of special interest
- TEAEs leading to discontinuation of study drug
- TEAE leading to death

Additional AEs may be considered for tabulation/summary based on recommendations from Clinical and Safety as deemed appropriate.

For TEAEs of special interest, the point estimate and 95% CI (using normal approximation) will be provided for the treatment difference in AE percentage between each Upadacitinib dose group and the combined placebo group.

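### The normal-approximation interval for the long-term AESI rate difference breaks down when placebo, with about 11 patient-years, has no events: it can wrongly exclude zero in up to 30% (1 year) or 65% (3.5 years) of cases, depending on the event rate.

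*SAP*

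**What the plan says.** SAP 10.2.3.1 gives event rates per 100 PY, with repeat events in one subject counted and days on drug divided by 365.25 as denominator. For AESIs it adds that "the point estimate and 95% CI (using normal approximation) will be provided for the treatment difference in AE rate per 100 patient-years". The contrast is of every dose with the three placebo arms taken together. The section does not name the variance, and it has no provision for zero or small counts.

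SAP 10.2.3 assigns events and exposure to the treatment received at the time. The 7.5 mg group therefore pools "subjects starting on Upadacitinib 7.5 mg QD and subjects switching from placebo to Upadacitinib 7.5 mg QD", and the other doses are built the same way. Placebo contributes Period 1 only.

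SAP 10.2.3.3 works by category, saying that "the Adverse Events of Special Interests (AESI) rate per 100 patient-years of exposure will be calculated overall, for each SOC and each PT", but states no interval there. Protocol 8.1.5.2.1 sets the quantity: "Event rate (per 100 patient years) for AEs of special interest will also be summarized for the combined safety analysis".

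Follow-up at each analysis is open. SAP 4.4 says "Additional unblinded analyses may be conducted for the purpose of regulatory submission", and Protocol 5.6.4 describes doses "dosed for approximately 3 years and half are expected to be efficacious".

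For Period 1, SAP 10.2.2.1 uses the same approach for percentages, again with placebo as comparator: "the point estimate and 95% CI (using normal approximation) will be provided for the treatment difference in AE percentage between each Upadacitinib dose group".

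**The concern.** A normal-approximation interval for a difference of two Poisson rates needs a reasonable count in both groups. Here one group is fixed at about 11 PY and the other keeps growing, so zero placebo events is a likely result for an uncommon AESI. The unpooled formula then treats the placebo rate as known to be exactly zero, although 11 PY says very little about it. As drug exposure accumulates, the background events that any group would show are enough to push the interval above zero.

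This is the only long-term AESI contrast with placebo in SAP 10.2.3, and the further unblinded analyses are meant for regulatory submission. A reader would take an interval wholly above zero as evidence of excess risk on drug.

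**Working it through.** **Plan's own figures.** The documents state no coverage or error rate for this interval. The figure that drives exposure is 48 per group (Protocol 8.2, SAP 4.3). Its basis reproduces: 46% against 80% with 90% power and a continuity correction gives 46 per group, and 46/0.95 = 48.4.

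**Exposure, assuming no drop-out**
- Placebo: 3 × 16 = 48 subjects for 84 days. 48 × 84 / 365.25 = 11.04 PY.
- Each dose at *t* years: 48*t* + 16(*t* − 84/365.25), which is 60.3 PY at 1 year, 124.3 at 2 years and 220.3 at 3.5 years. The 1- and 2-year cuts are assumptions; 3.5 years comes from Protocol 5.6.4.

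**Interval.** With *x* events in *A* PY on drug and *y* events in *P* PY on placebo, the usual form is

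*x*/*A* − *y*/*P* ± 1.96 √(*x*/*A*² + *y*/*P*²).

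If *y* = 0, this is (*x* ± 1.96√*x*)/*A*. It lies above zero when *x* > 1.96√*x*, that is for *x* ≥ 4 (4 > 3.92), whatever *A* is.

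**One rate by hand.** Take 3 per 100 PY in both groups at 3.5 years.
- No placebo event: exp(−0.03 × 11.04) = 0.718.
- Expected drug events: 0.03 × 220.3 = 6.61, so P(at least 4) = 0.896.
- Product: 0.718 × 0.896 = 0.643, a false exclusion of zero in 64%.

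**Full enumeration.** Independent Poisson counts with equal true rates; chance that the 95% interval excludes zero:

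| Rate per 100 PY | 1 year | 2 years | 3.5 years |
|---|---|---|---|
| 0.5 | 0.0% | 0.4% | 2.4% |
| 1 | 0.3% | 3.4% | 16.2% |
| 2 | 2.8% | 19.2% | 51.5% |
| 3 | 7.9% | 36.8% | 64.3% |
| 5 | 20.5% | 49.9% | 57.3% |
| 8 | 29.4% | 41.0% | 41.4% |
| 10 | 28.4% | 33.2% | 33.2% |
| 20 | 11.9% | 11.6% | 11.3% |
| 50 | 7.4% | 8.2% | 8.7% |

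The maxima are 29.5% at 1 year (rate about 8.5), 49.9% at 2 years (about 5) and 64.7% at 3.5 years (about 3.3). At 3.5 years the error exceeds 25% for rates from about 1.3 to 12.5 per 100 PY. Up to 10 per 100 PY nearly all of it comes from the case of no placebo events and points to harm on drug.

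**Example.** Four events in 220.3 PY against none in 11.04 PY:
- Normal approximation: (4 ± 3.92)/220.3 = 0.04 to 3.6 per 100 PY.
- Miettinen-Nurminen score interval: −33.0 to 4.7.
- Under equal rates, all four events fall on drug with probability (220.3/231.4)⁴ = 0.82, so the data are unremarkable.

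**Alternative.** At 3.5 years the score interval covers 93% to 96% over rates from 0.5 to 50 per 100 PY.

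**Period 1 percentages, 48 per arm (binomial enumeration).** Coverage is 76% at 2% vs 1%, 77% at 3% vs 1%, 90% at 5% vs 2%, 94.5% at 10% vs 5% and 94% at 20% vs 10%. With no events in either arm the interval is [0, 0]. With equal percentages of 1% to 5%, false exclusion is at most about 5%.

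**The case against.** - **Pooled reading.** AESIs are one line of the overview in SAP 10.2.3.1, and the category-level section has no interval. Summed over Table 13, which includes laboratory-type events, the rate could be much higher. If it were 20 to 80 per 100 PY (an assumption), the error at 3.5 years would be about 7% to 12%. This stands as a real ambiguity, but at 20 to 30 per 100 PY the error is still about twice the nominal 5%.
- **Maxima over an unknown rate.** This also stands. Very rare categories show almost no false exclusion (0.5% at 0.3 per 100 PY at 3.5 years); the trouble lies at intermediate rates.
- **Unspecified variance.** The SAP does not say unpooled. A test of zero difference with a pooled variance has a maximum error of about 7% on the same exposures. Unpooled is the usual default for an interval, so the silence is itself a reason to specify the method.
- **Drop-out.** Drug exposure will be lower than assumed. At 90%, 75% and 60% of it, the 3.5-year maximum is 62%, 58% and 52%, and the 1-year maximum is 27%, 22% and 17%. The size falls; the conclusion does not change.
- **Limited consequence.** No p-value, threshold or decision rule is attached, event counts and PY are shown beside the rate, and the error runs towards signalling harm rather than hiding it. This is right and limits the seriousness, but visible counts do not make the interval correct.
- **Period 1.** The low coverage at 2% vs 1% comes almost wholly from no events in either arm (probability 23%), and few readers would be misled by it. That part is minor.

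**Conclusion.** The concern holds. As written, the long-term interval does not have its nominal coverage when placebo has no events. Its false exclusion of zero reaches 30%, 50% and 65% at 1, 2 and 3.5 years at the least favourable rates, and stays near or below nominal for very rare events. These figures assume unpooled variance, full retention, equal true rates and independent events. Repeat events in one subject, which the SAP counts, were not modelled. AESI rates and data cuts are not in the documents, so the error is a range, not an expected value. The primary analysis is untouched. The point should be fixed because these intervals would accompany the long-term safety comparison with placebo.

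**What to change.** - In SAP 10.2.3.1, replace the normal approximation with a Miettinen-Nurminen score interval for the event-rate difference, keeping the protocol's event rate as the estimand. It is defined at zero counts: none against none at 3.5 years gives −34.8 to 1.7 per 100 PY.
- Show an exact Poisson 95% interval beside each group's rate. For no events in 11.04 PY the upper limit is 3.689/11.04, or 33.4 per 100 PY, which makes the weakness of the placebo information plain.
- State whether the difference is given for all AESIs pooled, for each Table 13 category, or both.
- In SAP 10.2.2.1, use a Miettinen-Nurminen or Newcombe interval for the percentage difference. By Newcombe, 0/48 against 0/48 gives −7.4 to 7.4 percentage points.

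The cost is SAP wording and minor standard programming, with no change to conduct or sample size. The intervals will be wider, which is the honest reflection of 11 PY on placebo.

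### The long-term AESI rate difference sets up to years of upadacitinib against Weeks 0–12 of placebo, so it is biased if AESI rates, detection or case mix change over time

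*SAP*

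**What the plan says.** SAP 10.2.3 states that the long-term adverse event analysis "will be based on the actual treatment received at the time of AE occurrence", and it sets up four groups: the three doses and placebo. For the lowest dose it explains: "This includes AEs occurred under Upadacitinib 7.5 mg QD exposure from subjects starting on Upadacitinib 7.5 mg QD and subjects switching from placebo to" that same dose. The two higher doses are defined in parallel. Under SAP 10.2.3.1 the denominator of each rate is "the total number of days exposed to study drug summed across all treated subjects divided by 365.25", and in the numerator "a subject can contribute more than one event to the numerator".

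The same section then adds, for AESIs, that "the point estimate and 95% CI (using normal approximation) will be provided for the treatment difference in AE rate"; the quantity in full is the "treatment difference in AE rate per 100 patient-years between each Upadacitinib dose group and the combined placebo group". Nothing there limits the events or exposure to Period 1, adjusts for time on study, or warns the reader about either.

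Other passages fix the timing:
- Protocol 5.1: placebo is given for 12 weeks. Placebo subjects who continue are then switched to one of the three doses, and Period 2 runs until approval in Japan.
- Protocol 5.6.4: dosing is expected to last roughly three and a half years.

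Two more bear on the consequence:
- SAP 10.2.2.1, for Period 1 only, gives the "treatment difference in AE percentage between each Upadacitinib dose group and the combined placebo group" with a 95% CI.
- Protocol 8.1.5.2.1 asks only that AESI rates be summarised for the two periods combined. It mentions no difference from placebo.

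**The concern.** A rate per 100 PY allows for one group having more exposure than another. It does not allow for the exposure falling in a different part of the study. Here all placebo time is early, and most upadacitinib time is late.

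The documents give reasons to expect that early and late time differ:
- **TB detection.** In Period 1, TB testing after Screening is done at premature discontinuation but not at Week 12 (Protocol Table 2, note h). In Period 2 it is annual, and any positive screen is to be reported as an adverse event (Protocol 5.3.1.1). Tuberculosis is an AESI in SAP Table 13, although the SAP does not say whether its query captures latent TB.
- **Laboratory detection.** The Period 1 laboratory windows are Weeks 2, 4, 8 and 12 (SAP Table 5). After Week 24, visits are 12 weeks apart (Protocol 5.1). Anemia, neutropenia, lymphopenia and CPK elevation are all AESIs.
- **Background therapy.** Injected corticosteroids and higher oral doses are barred up to Week 24 (Protocol 5.2.3.3). From Week 24, injections and changes to background RA therapy are allowed (Protocol 5.2.3.2). Only upadacitinib time contains that phase.
- **Who remains.** From Week 24, subjects without 20% improvement in both joint counts at two consecutive visits are discontinued (Protocol 5.4.1).

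These can pull in opposite directions. The risk is that a dose-minus-placebo figure with a CI, printed beside the Period 1 comparison, is read as a drug effect when it partly reflects time on study.

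**Working it through.** The plan gives no AESI rate, precision or power, so there is no stated figure to reproduce. The check covers exposure and expected values.

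**Inputs from the documents.** 48 subjects start on each dose. There are 3 × 16 = 48 placebo subjects, of whom 16 move to each dose. Placebo lasts 12 weeks = 84 days, or 84/365.25 = 0.230 years. Follow-up F is about 3.5 years (Protocol 5.6.4); 1 and 2 years are shown as well.

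**Assumptions.** No drop-out. The drug has no effect. The background AESI rate is r1 per 100 PY in study Weeks 0–12 and r2 afterwards.

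**Step 1: exposure.**
- Placebo: 48 × 84/365.25 = 11.04 PY, all in Weeks 0–12.
- Each dose: 48F + 16(F − 0.230) PY.
- Share w of a dose group's time that falls in study Weeks 0–12: 11.04 divided by that total.

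| F (years) | PY per dose | Multiple of placebo | w |
|---|---|---|---|
| 1 | 60.3 | 5.5 | 18.3% |
| 2 | 124.3 | 11.3 | 8.9% |
| 3.5 | 220.3 | 20.0 | 5.0% |

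**Step 2: expected difference for a drug with no effect.** The placebo rate is r1. The dose-group rate is w·r1 + (1 − w)·r2. The difference is therefore (1 − w)(r2 − r1).

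| r1 then r2 (per 100 PY, assumed) | F = 1 | F = 3.5 |
|---|---|---|
| 20 then 10 | 0.817 × (−10) = −8.2 | 0.950 × (−10) = −9.5 |
| 10 then 20 | +8.2 | +9.5 |
| 3 then 1.5 | −1.23 | −1.42 |
| 3 then 6 | +2.45 | +2.85 |
| 3 then 3 | 0 | 0 |

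**Step 3: restrict to Period 1.** Every group then has 11.04 PY from the same study weeks. The expected difference for a drug with no effect is r1 − r1 = 0, whatever happens after Week 12.

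**The case against.** The strongest reply is that the SAP already holds the right comparison. The AESI percentage difference in 10.2.2.1 is concurrent, precedes any switching and answers the Period 1 safety objective. That stands. A reader might infer that 10.2.2.1 shares the flaw, but it does not; it limits the consequence. It still leaves the 10.2.3.1 figure uncorrected.

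A reader might also infer that the SAP presents the long-term contrast as randomised. It does not: SAP 10.1 separates long-term from Period 1 safety and says the former accounts for switching, and 10.2.3.1 specifies no test or p-value. The defect is a descriptive difference without a restriction or caveat.

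Nor do the documents show that misleading contrasts will be printed for malignancy or cardiovascular events separately. In 10.2.3.1 AESIs are one category in an overview list, and 10.2.3.3, which tabulates individual AESIs, asks for rates only. Opposing trends within a combined line could partly cancel.

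The size does rest on assumed rates, and the bias is zero if the rate is constant. Early drug intolerance could not serve as an illustration, because it is itself a drug effect. If early time were counted from first upadacitinib dose, the switchers' first 12 weeks would also be early: 64 × 0.230 = 14.7 PY, or 6.7% rather than 5.0% at 3.5 years, a small change. Drop-out would shorten exposure and move the result towards the 1-year column.

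Finally, false signals from the interval are not symmetric. With Poisson counts and a Wald interval (the SAP gives no variance formula), the CI lay wholly below zero in at most about 5% of cases across the no-effect scenarios tried, but wholly above zero in up to about 72%. The latter is driven mainly by zero placebo events. That is a separate interval problem, which arises even at a constant rate, and the bias described here does not depend on it.

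**Conclusion.** The point holds as a limited one. SAP 10.2.3.1 requires a non-concurrent difference from placebo whose expected value for an inert drug is (1 − w)(r2 − r1), with 1 − w between 0.82 and 0.95 for follow-up of 1 to 3.5 years. Most of any change in the background rate over time therefore passes straight into the reported difference. The exposure figures assume no drop-out; the rates are illustrative.

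The documents make a change in detection, background therapy or case mix plausible. They do not establish its direction or size, so it cannot be said that the output will favour or disfavour upadacitinib. The Period 1 comparison with placebo is unaffected.

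The difference is also out of step with the rest of the plan. Long-term efficacy has no statistical testing and keeps the placebo-switch sequences separate (SAP 9.1.1). The long-term laboratory and vital-sign sections (SAP 10.3.3 and 10.4.3) do not carry over the between-group tests used for Period 1.

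**What to change.** In SAP 10.2.3.1, delete the dose-minus-placebo AESI rate difference and its CI. Alternatively, restrict its events and exposure to Period 1 in every arm. Present long-term AESI rates by dose descriptively, in line with Protocol 8.1.5.2.1.

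If the placebo rate stays in the long-term tables, label it as Weeks 0–12 only and not concurrent with the upadacitinib rates, and refer the reader to 10.2.2.1 for the comparison with placebo.

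Deletion is the simpler choice. A Period 1 rate difference would largely repeat 10.2.2.1, and it would need a new table, because the Period 1 sections tabulate numbers and percentages rather than rates.

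The cost is SAP wording and a few table shells; data collection and conduct do not change. The downside is that the only contrast with placebo is then the shorter, less precise Period 1 one, on about 11 PY per group.
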